7.12 REPORTING DEVICE-RELATED COMPLAINTS OR DEFICIENCIES

All product complaints that meet the definition of device deficiency must be reported to the Sponsor within 10 days of discovery, with the exception of SAEs which require 24-hour reporting. The error reporting or complaint form must be completed and emailed to the Sponsor at [contact].

Device deficiencies include malfunctions, misuse or use errors and inadequate labeling. A malfunction is defined as the failure of a device to meet its performance specifications or otherwise perform as intended. The intended performance of a device refers to the intended use for which the device is labeled or marketed.

Any problems experienced during the treatment procedure including potential malfunctions of the device, error messages displayed on the device screen following treatment, or errors that occur during the treatment procedure must immediately be reported to the Sponsor or its designee for evaluation.

7.13 NOTIFYING REGULATORY AUTHORITIES AND INSTITUTIONAL REVIEW BOARDS (IRBs)/RESEARCH ETHICS BOARDS (REBs)/ETHICS COMMITTEES (ECs) OF SAFETY INFORMATION**7.13.1 SPONSOR RESPONSIBILITIES**

- Determine whether the safety information meets the requirements for expedited reporting to the applicable regulatory authorities
- Prepare and submit the safety report to the applicable regulatory authorities
- Send all participating PIs a safety report and Investigator Safety Letter (i.e., Dear Investigator Letter) that will include a statement if there is or is not any significant new safety information that might influence the risk-benefit assessment of the IP and/or study device, sufficient to consider changes in product administration or overall conduct of the clinical investigation

7.13.2 PRINCIPAL INVESTIGATOR (PI) RESPONSIBILITIES

- Forward a copy of the safety report and Investigator Safety Letter (i.e., Dear Investigator Letter) to their IRB/REB/EC as soon as practical in accordance with the governing policy and/or procedures
- Notify their IRB/REB/EC of safety information (i.e., SAEs, pregnancies and AESIs) that occur at their clinical trial site in accordance with their local institutional policy

7.14 POST-TRIAL REPORTING REQUIREMENTS

PIs are not obligated to actively seek AEs or SAEs beyond the clinical trial reporting period. However, if the PI becomes aware of an AE or SAE that occurs after the Completion or Termination Visit and the event is deemed by the PI to be probably or possibly related to the clinical trial treatment, the PI should promptly document and report the event to the Sponsor. Additionally, if the trial is discontinued for any reason (Section 7.15), all enrolled subjects still participating in the study will undergo the end of study evaluation prior to discontinuation from the study and any reported SAE or AESI will be followed by the PI until resolution or return to baseline status, or stabilization of the reported event (i.e., the expectation that it will remain chronic).

7.15 CLINICAL TRIAL DISCONTINUATION

INOVIO reserves the right to discontinue the clinical trial at this site or at multiple sites for safety or administrative reasons at any time. In particular, a clinical trial site that does not recruit at a reasonable rate may be discontinued. Additionally, the clinical trial may be discontinued at any time by an IRB/REB/EC, INOVIO, or a regulatory authority as part of their duties to ensure that clinical trial participants are protected.

If the clinical trial is discontinued and/or the clinical trial site closed for any reason, all IP and devices must be returned to INOVIO or its representative. The PI should ensure that their site file documents are complete prior to archiving, and provide copies of any requested documents to INOVIO for its Trial Master File (TMF).

8.0 STATISTICAL CONSIDERATIONS

8.1 STATISTICAL AND ANALYTICAL PLAN

The documentation of the statistical and analytical plan is presented below.

8.2 GENERAL CONSIDERATIONS

The statistical analysis of the data will be performed by Inovio Pharmaceuticals, or its representative. This is a randomized across Study Group, investigator-and-participant blinded, placebo-controlled (SSC-0001), multi-center phase 2a trial to evaluate the safety, tolerability and immunological profile of INO-4700 administered in healthy adult volunteers. Approximately 542 volunteers will be evaluated across two (2) parts: Part 1 Dose Finding and Part 2 Expansion.

Approximately 192 participants in Part 1 will be randomized across each group (A through I; see [Table 1](#)) to receive either INO-4700 or placebo. Upon completion of the Week 10 visit by all Part 1 participants including evaluable immunological data from all Study Groups, one optimal Study Group dose and regimen will be selected for expansion into Part 2. Participants in Part 1 will be followed until Week 48.

Approximately 350 participants in Part 2 will be randomized to receive the optimal dose of INO-4700 or placebo (see [Table 2](#)). The first 225 participants randomized in parallel to three Study Groups will receive a third dose of either INO-4700 or placebo at Week 48. Participants will either receive a week 48 active treatment administration on top of their two prior active treatment administrations (N=100), or a week 48 placebo administration on top of their two prior active treatment administrations (N=100) or a week 48 placebo administration on top of two prior placebo administrations (N=25). Collectively, these first 225 participants will be followed until Week 68. The remaining 125 participants will be randomized in parallel to either 2 active treatment administrations (N=100) or 2 placebo administrations (N=25) and followed until Week 48.

Details on the Study Group design and conduct and frequency of DMSB meetings can be found in [Sections 3.0](#) and [12.1](#).

The trial's primary analyses pertains to the evaluation of the tolerability, safety and overall immune response to INO-4700 administered by ID injection followed by EP in healthy volunteers. Exploratory analyses concern the evaluation of the expanded immunological response to INO-4700 delivered by ID injection followed by EP, the cellular (T cell) and humoral immune response to boosting with a third INO-4700 ID injection followed by EP and the evaluation of the cross reactivity of other coronavirus spike proteins to the humoral

immune response to the MERS-CoV spike protein after receipt of the INO-4700 ID injection followed by EP.

8.3 STATISTICAL HYPOTHESES

No formal statistical hypothesis will be tested in Part 1 of this trial. The hypothesis in Part 2 of this trial is $H_0: p \leq 70\%$ versus $H_1: p > 70\%$, where p denotes the true population overall immunological response rate for the selected optimal dose of INO-4700.

8.4 ANALYTICAL POPULATIONS

Analysis populations will be:

The modified intention to treat (mITT) population includes all participants who receive at least one dose of the INO-4700 or placebo. Participants in this sample will be analyzed by their original assigned dose of INO-4700 or placebo. The mITT population will be used to analyze co-primary and exploratory immunological endpoints.

The per-protocol (PP) population is comprised of mITT participants who receive all their planned administrations and who have no Medical Monitor-assessed important protocol violations. Analyses on the PP population will be considered supportive of the corresponding mITT analyses. Participants excluded from the PP population will be identified and documented prior to locking the study database.

The safety analysis population includes all participants who receive at least one dose of INO-4700 or placebo administered by ID injection. Participants for this population will be grouped in accordance with the dose of INO-4700 or placebo that they received. This population will be used for all safety analyses in the study.

8.5 DESCRIPTION OF STATISTICAL METHODS

8.5.1 PRIMARY SAFETY ANALYSES

The primary analyses for this trial are safety analyses of treatment emergent adverse events (TEAEs), administration site reactions and clinically significant changes in safety laboratory parameters from baseline.

TEAEs are defined for this trial as any AEs/AESIs/SAEs that occur on or after Day 0 following IP administration. All TEAEs will be summarized by frequency, percentage and associated 95% Clopper-Pearson confidence interval, and in Part 2, the difference in the percentage between those who received INO-4700 and their corresponding same regimen placebo together with associated 95% confidence interval. Related SAEs and related Grade 3 or higher AEs will also be analyzed as described above within and between associated placebo in part 1. The frequencies will also be presented separately by dose number and will be depicted by system order class and preferred term. Additional frequencies will be presented with respect to maximum severity and relationship to IP. Multiple occurrences of the same AE in a single subject will be counted only once following a worst-case approach with respect to severity and relationship to IP. All serious TEAEs will also be summarized as above. AE duration will be calculated as AE stop date – AE start date + 1 day. AEs and SAEs that are not TEAEs or serious TEAEs will be presented in listings.

All of these primary safety analyses will be conducted on the participants in the safety population.

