8.5.9 EXPLORATORY ANALYSES

T and B post baseline cell number will be analyzed descriptively by Study Group using the mean or median and associated 95% confidence intervals.

In Part 2, treatment difference comparisons will include a comparison of two dose INO-4700 participants who are boosted with INO-4700 versus two dose INO-4700 participants who are boosted with placebo.

Exploratory ANCOVA and Logistic models may be fit that include baseline, confounder variables such as age, antibodies to other coronaviruses and gender to test the relationship between study group and different immune response variables. The relationship between antibodies to other coronaviruses and humoral immune responses will be explored using regression methods such as linear regression.

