4.3.2.2. Adverse Events

All AEs will be coded using the MedDRA SOC and PT coding system (v. 23.0) and displayed in tables by study and treatment groups and by subject in data listings.

Analyses of AEs will be performed for those events that are considered treatment-emergent, where treatment-emergent adverse events (TEAEs) are defined per protocol as any adverse event with onset after the administration of study medication through the end of the study (Week 68), or any event that was present at baseline but worsened in intensity or was subsequently considered drug-related (definite, probable, or possible relationship) by the Investigator through the end of the study.

Laboratory AEs will be assessed and graded in accordance with the “Toxicity Grading Scale for Healthy Adult and Adolescent Volunteers Enrolled in Preventive Vaccine Clinical Trials”, issued in September 2007 (see Protocol [Appendix A](#)).

Adverse events will be summarized by participant incidence rates; therefore, in any tabulation, a participant contributes only once (i.e., the most related occurrence or the most intense occurrence) to each of the incidence rates in the descriptive analysis, regardless of the number of episodes.

All TEAEs will be summarized by frequency, percentage, and, in Part 2, by the difference in the percentage between those who received INO-4700 and their corresponding regimen placebo.

Related SAEs and related Grade 3 or higher AEs will also be analyzed as described above within and between associated placebo in Part 1. The frequencies will also be presented separately by dose number and will be depicted by SOC and PT. Additional frequencies will be presented with respect to maximum severity and relationship to IP. Multiple occurrences of the same AE in a single participant will be counted only once following a worst-case approach with respect to severity and relationship to INO-4700. All serious TEAEs will also be summarized as above.

No formal hypothesis-testing analysis of adverse event incidence rates will be performed.

By-participant listings will be provided for all AEs, participant deaths, SAEs, and AEs leading to withdrawal.

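### Part 2 plans no adverse-event difference with CI between Active-Booster and Active-Placebo, the randomised contrast that isolates the third dose

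*Protocol*

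**What the plan says.** **The planned difference.** Protocol 8.5.1 summarises treatment-emergent AEs by frequency and percentage with a Clopper-Pearson interval. For Part 2 it adds "the difference in the percentage between those who received INO-4700 and their corresponding same regimen placebo", with a 95% CI. SAP 4.3.2.2 has the same contrast, "by the difference in the percentage between those who received INO-4700 and their corresponding regimen placebo", in a sentence that does not mention an interval. Output by dose number is described as frequencies only.

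**The arms.** Protocol 8.2 states: "The first 225 participants randomized in parallel to three Study Groups will receive a third dose of either INO-4700 or placebo at Week 48". The groups, also in Table 3, are Active-Booster (two active doses, then active; N=100), Active-Placebo (two active doses, then placebo; N=100) and three-dose placebo (N=25).

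**Where the two primed arms are compared.** Protocol 8.5.9, under exploratory analyses, includes a "comparison of two dose INO-4700 participants who are boosted with INO-4700 versus two dose INO-4700 participants who are boosted with placebo". It names no endpoint. Protocol 8.2, the boosting objective in Protocol 3.3 and the booster endpoints in SAP 1.2.5.3 all describe this work as immune response.

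**Grouping.** Protocol 8.4 groups the safety population by the product actually received. SAP 3.2 lists Active-Booster and Active-Placebo as separate Part 2 groups, then says that active and placebo data will be pooled and summarised. SAP 4.3.2 tabulates Part 2 safety by treatment group.

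**The concern.** Active-Booster and Active-Placebo are randomised against each other and share the same two priming doses, the same Week 48 visit and the same injection and electroporation procedure. They differ only in what is in the third syringe. A difference between them in events after Week 48 is therefore attributable to the third active dose. The plan sets up this comparison but specifies no AE difference or interval for it.

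The contrast that is specified can be read in three ways for third-dose events:

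- Active-Booster against the 25 three-dose placebo participants. This is the most natural reading. The control is small and unprimed.
- All 200 primed three-dose participants against those 25. Half of the active side would have had placebo at the visit in question.
- Active-Booster against everyone given placebo at Week 48 (100 + 25 = 125). This mixes primed and unprimed controls.

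At stake are the precision of the third-dose safety estimate and what it can be attributed to. Safety is a primary analysis, and the version 2.0 summary of changes says that AE collection was extended to improve safety assessment after the booster. Protocol 3.5 and 7.9 accordingly collect all AEs to study discharge.

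**Working it through.** **The plan's own safety figures.** The only safety sizing (Protocol 8.6, SAP 3.1) is a set of zero-event limits for serious AEs. The exact two-sided 95% upper limit with no events is 1 − 0.025^(1/n): 10.9% for n=32, 2.28% for n=160 and 0.80% for n=460. These agree with the stated limits of <11%, <3% and <1%. No precision is stated for any between-group AE difference.

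**Inputs.** Arm sizes of 100, 100 and 25 come from Protocol 8.2 and Table 3. No Part 2 AE rate is given, so a range is assumed. Its top, 63%, is close to the 63.3% erythema rate reported for intradermal dosing in Protocol 1.4.

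**Standard-error multiplier**, √(1/n₁ + 1/n₂):

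- 100 v 25: √(0.01 + 0.04) = 0.224
- 100 v 100: √(0.01 + 0.01) = 0.141
- Ratio: √(0.05/0.02) = 1.58

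The ratio does not depend on the common rate. A 100 v 25 comparison carries the information of 2/0.05 = 40 per arm.

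**95% half-width**, 1.96 × √[p(1 − p)(1/n₁ + 1/n₂)], in percentage points:

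| Assumed common rate | 100 v 25 | 100 v 100 |
|---|---|---|
| 2% | 6.1 | 3.9 |
| 10% | 13.1 | 8.3 |
| 30% | 20.1 | 12.7 |
| 63% | 21.2 | 13.4 |

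At 30%, for example, 1.96 × √(0.21 × 0.05) = 0.201 and 1.96 × √(0.21 × 0.02) = 0.127.

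**The other two readings.** With 200 v 25 the half-width at 30% is 19.1 points. An excess d confined to the boosted participants also shrinks to d × 100/200 = d/2, so a 20-point excess would appear as 10. With 100 v 125 the half-width at 30% is 1.96 × √[0.21 × (0.01 + 0.008)] = 12.1 points. Precision is not the problem there. The control group combines 100 primed and 25 unprimed people, so the contrast no longer holds priming constant.

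SAP 4.3.2.2 rules out formal testing of AE rates, so interval width is the relevant measure and no power figures are given.

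**The case against.** The strongest reply is that little is missing. SAP 3.2 gives each primed arm its own column, SAP 4.3.2 tabulates safety by treatment group, and Protocol 8.5.1 presents frequencies by dose number. A reader could set the two arms side by side and subtract. This stands as far as it goes. One might infer that the Active-Placebo safety data go unused, and the documents do not support that. What is absent is a planned difference with its interval.

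Two other readings are also too strong. Protocol 8.5.1 gives no comparator size, so the 25 is inferred from the same-regimen wording and the arm sizes; grouping by product received leaves 100 v 125 possible. Nor is pooling of the 200 primed participants prescribed. The pooling sentence in SAP 3.2 leaves it open but does not say that it governs third-dose events or replaces the separate groups. The reply therefore weakens a claim that the plan fixes a poor comparator, but it confirms that the comparator needs stating.

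Protocol 8.5.9 could be read to cover safety because it names no endpoint. Its setting makes immune response the likely meaning, though no sentence excludes AEs. Even on the wider reading, the comparison would be exploratory while safety is primary.

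Finally, the comparison with never-vaccinated participants answers a legitimate question about the whole three-dose regimen and should not be displaced.

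**Conclusion.** The point holds in this form: the single planned Part 2 AE difference is ambiguous for third-dose events, and no difference with CI is specified between the two randomised arms that isolate the third dose. On the most natural reading, the resulting interval is 1.58 times as wide as the one that the same participants could provide. Over assumed common rates of 2% to 63%, the half-width is 6.1 to 21.2 points instead of 3.9 to 13.4. The ratio rests on the planned arm sizes and a common event rate; the half-widths also rest on the assumed rates and a normal approximation. The loss from pooling applies only if pooling is what was meant.

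A reader might infer that the trial's booster safety findings are compromised. They are not. Item 1 of the later administrative memo (approved January 2023) records that the trial would not proceed to Part 2. This is a flaw in the plan, cheap to correct, and it affects no reported result.

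**What to change.** In Protocol 8.5.1 and SAP 4.3.2.2:

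1. For AEs and injection-site reactions with onset after the Week 48 dose, add Active-Booster minus Active-Placebo, with 95% CI, as the planned third-dose safety contrast.
2. State that these two arms are not pooled as INO-4700 for events after Week 48, and qualify the pooling sentence in SAP 3.2 to match.
3. Keep the comparison with the 25 three-dose placebo participants as a separate whole-regimen contrast, and name its arms.

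The cost is a sentence or two in each document and one table. It needs no extra participants, visits or samples. Because the contrast is added and nothing is replaced, no existing comparison is lost.

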8.5.2 PRIMARY IMMUNOGENICITY ANALYSES

For both Part 1 and Part 2, antigen specific binding antibody titers, MERS-CoV neutralizing antibody titers, and specific cellular immune responses will be analyzed by Study Group. Binding antibody titer will be analyzed for each Study Group using the geometric mean and associated 95% confidence intervals. Percent neutralizing antibodies and antigen specific cellular immune response increases will be analyzed for each Study Group using medians, inter-quartile range and 95% confidence intervals. Percentage with overall immune response, inclusive of seroconversion (i.e., positive titer), and corresponding 95% Clopper-Pearson confidence intervals will be analyzed within each Study Group.

In Part 1, the difference in percentage of overall immune responders including seroconverters between all pairs of INO-4700 Study Groups will be calculated along with corresponding exact 95% confidence intervals.

In Part 2, the primary hypothesis of $H_0: p \leq 70\%$ versus $H_1: p > 70\%$ will be tested with an exact test of a binomial proportion. In addition, the binding antibody titer difference between INO-4700 and placebo will be analyzed using the geometric mean fold ratio and associated 95% confidence interval. Percent neutralizing antibodies and antigen specific cellular immune response differences between INO-4700 and placebo will be analyzed using the difference in medians and associated 95% confidence intervals.

All of these primary immunogenicity analyses will be conducted on the participants in the mITT and PP populations.

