4.2 EXCLUSION CRITERIA

- a. Pregnant or breastfeeding, or intending to become pregnant or father children within the projected duration of the trial starting with the screening visit until 3 months following last dose;
- b. Positive serum pregnancy test during screening or positive urine pregnancy test prior to dosing;
- c. History of respiratory diseases such as asthma, chronic obstructive pulmonary disease or chronic bronchitis;
- d. Is currently participating in or has participated in a study with an investigational product within 30 days preceding Day 0;
- e. Previous receipt of any vaccine within 30 days preceding Day 0 or planning to receive any vaccine during the timeframe restricted per the protocol;
- f. Previous receipt of an investigational vaccine product for prevention of MERS;
- g. Prior exposure to MERS-CoV or camels (serology or antibody testing will be requested at the Investigator's discretion);
- h. Participants who participated in MERS-201 Part 1 cannot participate in MERS-201 Part 2;
- i. Fewer than two acceptable sites available for ID injection and EP considering the deltoid and anterolateral quadriceps muscles. The following are unacceptable sites:
 - Tattoos, keloids or hypertrophic scars located within 2 cm of intended administration site;
 - Implantable-Cardioverter-defibrillator (ICD) or pacemaker (to prevent a life-threatening arrhythmia) that is located ipsilateral to the deltoid injection site (unless deemed acceptable by a cardiologist);
 - Any metal implants or implantable medical device within the electroporation site;
- j. Prisoner or participants who are compulsorily detained (involuntary incarceration);
- k. Current or anticipated concomitant immunosuppressive therapy (excluding inhaled, topical skin and/or eye drop-containing corticosteroids) prior to dosing. Systemic corticosteroids must be discontinued at least 3 months prior to first dose;
- l. Reported active drug or alcohol or substance abuse or dependence.

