Urine samples will be tested by dipstick for glucose, protein, and hematuria at Screening and select visits during the study. If abnormal (presence of protein, hematuria, or glucose $\geq 1+$), a microscopic examination should be performed.

Serology:

Antibodies to MERS-CoV (per PI discretion), Hepatitis B surface antigen (HBsAg), Hepatitis C antibody and HIV antibody or rapid test will be measured at Screening only.

Pregnancy Testing:

For women of childbearing potential (WOCBP), a serum pregnancy test will be obtained at Screening and a urine pregnancy test will be performed prior to any dosing. A negative result for urine β -HCG (test must have a sensitivity of at least 25 mIU/mL) must be available prior to each administration of IP. If the β -HCG test is positive, indicating that the participant is pregnant prior to completing the specified dose regimen, then no further IP

will be administered. Every attempt should be made to follow pregnant participants for the remainder of the study and to determine the outcome of the pregnancy.

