6.4.6 PERIPHERAL BLOOD IMMUNOGENICITY ASSESSMENTS

Whole blood and serum samples will be obtained to assess overall immune response. Immunology blood and serum samples are to be collected at Screening and select visits during the study. Both Screening and Day 0 immunology samples are required to enable all immunology testing. However, at the Principal Investigator’s discretion, collection of the screening immunology samples may be postponed and collected along with the Day 0 samples. Details of the immunology sample collection and shipment information will be provided in the Laboratory Manual. The T and B cell immune responses to INO-4700 will be measured using assays that include but are not limited to ELISA, neutralization, assessment of immunological gene expression, assessment of immunological protein expression, flow cytometry and ELISPOT.

An immune responder is defined as having either an increase in vaccine antibody titer compared to baseline or an increase in the number of vaccine specific IFN-gamma secreting cells as compared to baseline.

Determination of analysis of collected samples for immunological endpoints will be determined on an ongoing basis throughout the study.

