8.6 SAMPLE SIZE/POWER

No formal power analysis is applicable to Part 1 of this trial, as descriptive statistics will be used to summarize the data.

For each Study Group in Part 1 of the trial with 32 INO-4700 administered participants, the study provides 95% confidence that the true incidence of SAEs is <11% if no SAEs are observed in a study group. For all the Study Groups combined in Part 1 of the trial with 160 INO-4700 administered participants, the study provides 95% confidence that the true incidence of SAEs is <3% if no SAEs are observed in this study phase. For all Study Groups combined across Parts 1 & 2 of the trial with 460 INO-4700 administered participants, the study provides 95% confidence that the true incidence of SAEs is <1% if no SAEs are observed.

For Part 2 of this trial, an evaluable sample of 260 active subjects treated with INO-4700, which will be used for formal hypothesis testing, provides >90% power to detect an INO-4700 overall immunological response rate of 70% or higher should this overall response rate truly be 80%, using a one-sided type 1 error rate of 0.025.

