4.3. Immunology, Safety, and Exploratory Evaluations

4.3.1. Immunology Evaluations

The following immunogenicity analyses will be conducted on participants in the PP and mITT study populations.

In Part 1, the difference in percentage of overall immune responders including seroconverters (i.e. positive titer) between all pairs of INO-4700 study groups will be calculated along with corresponding exact (Clopper-Pearson) 95% CIs. The T and B cell immune responses to INO-4700 will be measured using assays that include ELISA, neutralization, assessment of immunological gene expression, assessment of immunological protein expression, flow cytometry, and ELISPOT.

In Part 2, the primary hypothesis of $H_0: p \leq 70\%$ versus $H_1: p > 70\%$ will be tested with an exact test of a binomial proportion. In addition, the binding antibody titer difference between INO-4700 and placebo will be analyzed using the geometric mean fold ratio and associated 95% confidence interval. Percent neutralizing antibodies and antigen specific cellular immune response differences between INO-4700 and placebo will be analyzed using the difference in medians and associated 95% CIs.

For both Part 1 and Part 2, antigen specific binding antibody titers, MERS-CoV neutralizing antibody titers, antibodies to other coronaviruses, and specific cellular immune responses will

be analyzed by study group and treatment group, respectively. Time to peak post-baseline titers will be summarized using descriptive statistics. Binding antibody titer will be analyzed for each study group using the geometric mean and associated 95% CIs. Percent neutralizing antibodies and antigen specific cellular immune response increases will be analyzed for each study group using medians, inter-quartile range and 95% CIs. Percentage with overall immune response, inclusive of seroconversion and corresponding 95% Clopper-Pearson CIs will be analyzed within each study and treatment group.

All immunologic data will be presented in data listings.

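### Overall response is defined two ways: Protocol 6.4.6 requires a rise from baseline, while Protocol 8.5.2 and SAP 4.3.1 include a positive titer with no baseline condition

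*Protocol*

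**What the plan says.** **Responder rule.** Protocol 6.4.6: "An immune responder is defined as having either an increase in vaccine antibody titer compared to baseline", or alternatively a rise in the number of vaccine-specific IFN-gamma secreting cells. Both routes are changes from baseline.

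**Analysis wording.** Protocol 8.5.2 describes the reported quantity as "Percentage with overall immune response, inclusive of seroconversion (i.e., positive titer". SAP 4.3.1 does the same with "overall immune responders including seroconverters (i.e. positive titer". Neither attaches a baseline condition to the positive titer. SAP 1.2.5.2 lists overall immune response and its components without defining it, and the 6.4.6 rule appears nowhere in the SAP. SAP 3.4 defines baseline, but the responder wording does not use it.

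**Entry.** Protocol 4.2, criterion g, excludes "Prior exposure to MERS-CoV or camels (serology or antibody testing will be requested at the" investigator's discretion. The serology paragraph of Protocol 6.4 agrees: "Antibodies to MERS-CoV (per PI discretion".

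**Where the rate is used.** Protocol 8.5.6 sets a 70% overall immune response as the minimum for selecting a Part 1 dose. In Part 2 the null hypothesis p ≤ 70% "will be tested with an exact test of a binomial proportion", where p "denotes the true population overall immunological response rate for the selected optimal dose of INO-4700". No placebo rate is subtracted in either case.

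**The concern.** Take a participant who is MERS-antibody positive at Day 0, keeps the same titer after dosing and shows no T-cell rise. Under 6.4.6 this person is not a responder. Under a literal reading of 8.5.2 and SAP 4.3.1 the person has a positive titer and can be counted as one. The documents do not say which wording governs. A programmer working from the SAP alone would find only the second.

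Such a person can get in. Criterion g excludes recognised exposure, but without mandatory serology it cannot catch exposure nobody knew about. Protocol 1.2.3 itself cites an estimate that more than 62% of infected people may go undetected or have only mild symptoms. Neither the mITT nor the PP definition mentions baseline serostatus, and SAP 3.8 plans no subgroup analyses, so no planned table would separate these participants.

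Randomisation does not protect the two 70% criteria, because each compares an active-group rate with a fixed number. A baseline-positive participant counted without any change raises that rate directly.

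**Working it through.** **Inputs from the documents.** Null rate 70%, alternative 80%, one-sided alpha 0.025, 260 evaluable active participants (Protocol 8.3 and 8.6); 32 participants per active group and a 70% minimum in Part 1 (Protocol 8.6 and 8.5.6).

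**Input that is assumed.** b, the share of active participants seropositive at baseline. The documents give no value. I use 2% and 5% as illustrations.

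**Step 1: reproduce the plan's power.** Protocol 8.6 claims more than 90% power "should this overall response rate truly be 80%, using a one-sided type 1 error rate of 0.025". The smallest count c with P(X ≥ c | 260, 0.70) ≤ 0.025 is c = 197 (75.8%). Exact alpha is 0.0232, and power at 80% is P(X ≥ 197 | 260, 0.80) = 96.0%. The claim holds.

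**Step 2: the response rate under the 8.5.2/SAP wording.** Let r be the response rate under 6.4.6. If every baseline-positive participant is counted, the rate becomes

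r′ = r(1 − b) + b = r + b(1 − r).

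The addition b(1 − r) is a ceiling provided that baseline-positive participants meet 6.4.6 at least as often as the others. It also takes all of them to remain positive after dosing.

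**Step 3: Part 2 type I error at r = 70%, P(X ≥ 197 | 260, r′).**

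| b | r′ | P(reject) |
|---|---|---|
| 0 | 0.700 | 0.023 |
| 2% | 0.70 + 0.02 × 0.30 = 0.706 | 0.037 |
| 5% | 0.70 + 0.05 × 0.30 = 0.715 | 0.071 |

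**Step 4: Part 1 minimum at r = 65%.** 70% of 32 is 22.4, so 23 responders are needed.

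| b | r′ | P(X ≥ 23 of 32) |
|---|---|---|
| 0 | 0.650 | 0.268 |
| 2% | 0.65 + 0.02 × 0.35 = 0.657 | 0.296 |
| 5% | 0.65 + 0.05 × 0.35 = 0.6675 | 0.341 |

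**Step 5: differences between active groups.** With the same b in two groups, r₁′ − r₂′ = (1 − b)(r₁ − r₂). In expectation the difference shrinks slightly and is not tilted toward either group.

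**Step 6: the 6.4.6 reading.** A stable pre-existing titer adds no responders. The rate stays at r, alpha at 0.0232 and power at 96.0%, whatever b is.

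**The case against.** The strongest reply is that 6.4.6 is the only sentence that defines a responder. The wording in 8.5.2 is a reporting sentence with a parenthesis, and seroconversion ordinarily means going from negative to positive. On that reading nothing is inflated. This is a fair account of what was probably intended, but the parenthesis says something else, and the SAP carries the parenthesis without the rule. The ambiguity stands.

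A reader might infer that seropositive participants will in fact be counted as successes. The documents do not support that: it depends on which wording is applied, and under 6.4.6 it does not happen.

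A reader might also take the planned modelling of coronavirus antibodies as a sign that the sponsor expected MERS-seropositive enrolment. It is not. Protocol 8.5.9 refers to antibodies to other coronaviruses, in line with the exploratory cross-reactivity objective.

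The size can be overstated too. At b=10% the type I error would be 17.5%, but nothing in the documents supports a share that high once known MERS-CoV and camel exposure is excluded. Even 2% and 5% are only illustrations. The formula is close to a worst case: a previously primed person whose titer or T-cell count rises after dosing is already a responder under 6.4.6 and adds nothing.

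Response is reported in the placebo groups as well, and all immunologic data are listed, so background positivity is not wholly hidden. But Part 1 has only 32 placebo participants; at b=5% that is 32 × 0.05 = 1.6 expected positives, too few to measure it well.

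Finally, 6.4.6 sets no minimum size for the rise, so a stable positive titer could still count through assay variation. That is a limit of 6.4.6 that the change proposed here does not remove.

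**Conclusion.** The conflict in the primary immunogenicity endpoint is real and should be resolved. Under the 8.5.2/SAP wording the response rate could rise by up to b(1 − r): at r=70%, 0.6 percentage points for b=2% and 1.5 for b=5%. Part 2 type I error would go from 2.3% to at most about 3.7% or 7.1%. The chance that a Part 1 group with a true 65% rate reaches 23/32 would go from 27% to at most about 30% or 34%. These figures rest on assumed values of b and on the ceiling conditions in the working; under 6.4.6 the effect is nil.

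A reader might infer that the trial's decisions were distorted. They were not shown to be. The later protocol administrative memo states that the trial would not proceed to Part 2 and that no Part 1 dose group met the selection criteria. So no false go decision occurred, and the Part 2 figures describe a test that was planned but not run. What remains is that the reported Part 1 response rates depend on which definition is applied.

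**What to change.** - In Protocol 8.5.2 and SAP 4.3.1, replace the parenthetical gloss on seroconversion with *negative at baseline and positive post-dose*.
- State in the SAP that the 6.4.6 increase-from-baseline rule governs overall response, and that it is the only antibody route to response for a baseline-positive participant.
- Use the pre-dose immunology serum, which 6.4.6 already requires from everyone, to tabulate baseline-positive participants by study group and to repeat the responder analysis in baseline-negative participants.

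The cost is two wording changes and one extra table. No new samples are needed.
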